3.10.6. Subject Treatment Questionnaire Phone Visit (Visit 14)

The Subject Treatment Questionnaire Phone Visit (See Section 3.11.6) will be conducted via phone for subjects that are both currently enrolled and that have completed the study. The Phone Visit will be completed by independent consultant.

The Visit should be completed within three (3) months of the CIP v2.0 IRB approval. If the Visit cannot be completed in that timeframe, no further efforts will be made to complete the Visit. Non-completion of the Visit will not be deemed a protocol deviation.

The following procedures will be completed:

- Independent Consultant will follow IRB-approved script to explain purpose of the call and obtain verbal consent from the Subject.
- Upon receipt of Subject's verbal consent to participate, consent will be documented.
 - Note: If consent is not given, no further activities to be completed for this visit.
- Subject will be asked questions in the IRB-approved Subject Treatment Questionnaire.

Table 2. Schedule of Assessments

	Procedure Visit (Visit 2)				1 Day (phone interview) (Visit 3) (Range +2 days)	7-Day (office visit) (Visit 4) (Range ±2 days)	30-Day (office visit) (Visit 5) (Range ±7 days)	90-Day (office visit) (Visit 6) (Range ±14 days)	180-, 270-, and 365-Day (office visits) (Visit 7-9) (Range ±21 days)	15-, 21-month (office visit) (Visit 10-11) (Range ±30 days)	18-, 24-month (office visit) (Visit 12-13) (Range ±30 days)	Subject Treatment Questionnaire Phone visit (Visit 14)
	Screening (Visit 1)	Pre-Procedure	Procedure	Post-Procedure								
Eligibility criteria	X											
Baseline medical history	X											
Clinical evaluation	X	X		X		X	X	X	X	X	X	
Endoscopic assessment	X	X		X			X	X				
Study treatment provided			X									
Physician feedback on device usability			X									
Subject feedback on tolerability of procedure (Wong-Baker Pain Scale)			X									
Medication usage recorded	X	X			X	X	X	X	X	X	X	
Adverse events recorded			X	X	X	X	X	X	X	X	X	
Subject assessment of nasal symptoms (rTNSS)	X	X					X	X	X	X	X	
Subject satisfaction questionnaire								X				
Quality of life questionnaire (RQLQ)		X						X			X	
Concomitant Medications Updated	X	X			X	X	X	X	X	X	X	
Subject Treatment Questionnaire												X

3.11. Assessments

3.11.1. Clinical Evaluation

Investigators will conduct a clinical evaluation of study subjects at each study visit and findings will be documented.

Evaluation may be made by patient interview regarding their symptoms.

At the Screening, Procedure (pre- and post- procedure), 30 Day and 90 Day Visits, the evaluation will include physical exam of the treatment area under endoscope. The treatment

area will be assessed for bleeding, crusting, and swelling using a scale of 0 to 3 (0=None, 1=Mild, 2=Moderate, or 3=Severe). When endoscopic assessment is performed, photographic and/or video documentation will be obtained, if possible. An endoscopic exam may be completed beyond the 90-day time point at the discretion of the Investigator in the event of a study-related adverse event.

When possible, at the 180-, 270- and 365-Day and the 18- and 24-Month Follow-up visits, the clinical documentation will include an investigator’s assessment of improvement of symptoms of rhinitis since time of treatment with ClariFix device using a 7-point Likert¹² scale as follows:

- Very Much Improved
- Much Improved
- Minimally Improved
- No Change
- Minimally Worse
- Much Worse
- Very Much Worse

3.11.2. Wong-Baker FACES Pain Scale

Subject reported pain/discomfort at the time of treatment will be assessed using a 0 to 5-point Wong-Baker FACES pain scale¹³ (Figure 3).

Figure 3. 0 to 5-Point Wong-Baker FACES Pain Scale

3.11.3. Reflective Total Nasal Symptom Score (rTNSS)

The primary effectiveness endpoint will be assessed based on the four-symptom reflective Total Nasal Symptom Score^{14, 15} (rTNSS). rTNSS is a validated symptom severity scoring system that consists of the sum of four (4) individual subject-assessed symptom scores for rhinorrhea, nasal congestion, nasal itching, and sneezing. Each item is scored on a scale of 0 to 3 and is based on the subject’s evaluation of symptom severity over the preceding 24 hours at study visits. The four-symptom rTNSS has a possible score of 0-12.

Subjects will be asked to assess their symptoms at baseline (Procedure Visit) and at all follow-up points. The subjects will be asked to assess each symptom individually (runny nose, congestion, nasal itching, sneezing) in the following manner:

Please rate how your <symptom> has been over the past 24 hours

0 = None, no sign / no <symptoms> evident

1= Mild, sign/<symptom> present, but minimal awareness, easily tolerated

2= Moderate symptoms, definite awareness of sign/<symptom> that is bothersome but tolerable

3= Severe, (sign/<symptom> that is hard to tolerate, causes interference with activities of daily living and/or sleeping)

Subject may be reminded of baseline score prior to treatment, as appropriate.

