3.9.1. Pre-Procedure Evaluation

The baseline evaluation will take place on the day of the study procedure. All female subjects of childbearing potential will be asked to take a pregnancy test (urine). If the subject is pregnant,

they will not be considered eligible to participate in the study. If a subject becomes pregnant after the study treatment, during the study follow-up period, the subject shall be withdrawn from the study and will not undergo any further testing. The subject will be asked to rate their nasal symptoms using the rTNSS. If the subject does not meet the minimum symptom score requirement (**Table 1**, Inclusion criterion b), the subject will not be considered eligible to participate in the study.

If all the eligibility criteria are met, and the subject has signed the IRB-approved informed consent document, the subject shall be considered enrolled. The investigator and/or designee will document the subject's medical information on the Baseline CRF. Subjects will also complete the quality of life questionnaire (RQLQ) described in Section 3.11.4. Subjects shall then undergo treatment with the study device.

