5.2. Statistical Considerations

5.2.1. Statistical Overview

This trial is a prospective, single-arm, open-label, multi-center clinical evaluation of the safety and effectiveness of the ClariFix™ device when used to ablate unwanted tissue in the nose of subjects with chronic rhinitis. Effectiveness will be evaluated by analyzing the 90-day change from baseline in the 4-symptom rTNSS.

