5.2.2. Statement of Hypothesis

The statistical null hypothesis is that the mean 90-day within-subject change is zero; there is no effect of the device on rTNSS.

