5.2.5. Endpoint Analyses

In this single arm, open-label study, the focus of the primary efficacy endpoint analysis is on the magnitude and direction of change over 90 days in the 4-symptom rTNSS. The primary safety endpoint analysis is on the incidence of procedure- or device-related SAEs and UADEs over 90 days post-treatment (however, all AEs will be tracked and reported over the entire duration of the study). The statistical methodology is targeted to employ the paired sample t-test and/or its nonparametric equivalent, the Wilcoxon Signed Rank test. The two-tailed α -level is set at 0.05. No imputation of data will be performed.

All safety analyses will be performed on the Safety Population. All efficacy analyses will be performed on both the Efficacy and PP cohorts, as necessary.

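### Section 3.11.3 allows a reminder of the baseline rTNSS without naming a visit, and a single-arm trial has nothing to offset any effect on the ratings

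*Combined protocol and SAP*

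**What the plan says.** Section 3.11.3 defines the rTNSS as the sum of four subject-rated items, each scored 0 to 3, based on the subject's "evaluation of symptom severity over the preceding 24 hours at study visits". On timing it says "Subjects will be asked to assess their symptoms at baseline (Procedure Visit) and at all follow-up points". After the item wording it adds one last sentence: "Subject may be reminded of baseline score prior to treatment, as appropriate".

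Section 3.9.1 fixes when baseline is taken: "The baseline evaluation will take place on the day of the study procedure", and at that visit "The subject will be asked to rate their nasal symptoms using the rTNSS". The same rating decides eligibility, because a subject below the minimum in inclusion criterion b (Table 1) is not enrolled. Section 3.8 and Table 2 also schedule an rTNSS at screening, up to 30 days before the procedure.

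Sections 3.9.1 and 3.10 and Table 2 do not mention a reminder. No trigger, script or record of one is described.

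On the analysis, section 5.2.1 states "This trial is a prospective, single-arm, open-label, multi-center clinical evaluation", section 5.2.2 states "The statistical null hypothesis is that the mean 90-day within-subject change is zero", and section 5.2.5 says "the focus of the primary efficacy endpoint analysis is on the magnitude and direction of change over 90 days".

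**The concern.** The phrase about treatment can attach to the act of reminding or to the score. If it attaches to the act, the reminder happens before treatment. If it attaches to the score, the subject may be told the pre-treatment score when rating later. Either way, an earlier score may be disclosed around a rating that is meant to describe only the last 24 hours.

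At follow-up, a treated and unblinded subject who is told the old score may anchor on it, or may answer how much has changed instead of how severe symptoms are now. Before the procedure-day rating, the only score that exists is the screening score. Section 3.11.3 ties baseline to the Procedure Visit, so calling the screening score baseline would be loose usage, but nothing prevents it. A reminder of that score could move both the baseline value and the eligibility check.

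The primary result is a within-subject mean compared with zero. No comparator arm would carry the same effect, so a shift in either rating passes in full into the 90-day change. It also passes into the exploratory rTNSS changes and the responder rates in section 5.1.3.

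**Working it through.** **Which reading does the text favour?** Neither clearly.

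- *Reminder given before treatment.* Baseline is rated on the procedure day just before treatment, so reminding the subject of that same score serves little purpose. It would have a purpose only if the screening score were meant.
- *Reminder at a later rating.* This has an obvious use. But baseline is pre-treatment by definition, so the phrase about treatment then adds nothing.

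Each reading leaves something redundant, and no other section resolves it.

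**Inputs.** SD of within-subject change 2.5, two-sided alpha 0.05, 68 evaluable subjects and 90% power for one point (section 5.2.6). Pilot mean 6.2 at baseline and 2.7 at 90 days (section 1.2). The size of any reminder effect is not in the documents. I assume an average shift b, taken over all subjects, of 0.1, 0.25 or 0.5 point.

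**The plan's own figure.** The normal approximation gives n = [2.5 × (1.960 + 1.282) / 1]² = 65.7, so 66. With the noncentral t, power for one point is 0.897 at n=67 and 0.902 at n=68. The stated 68 therefore reproduces as the exact paired t-test answer.

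**Effect of an assumed shift when the mean change is otherwise zero.** The standard error is 2.5/√68 = 0.303. The half-width of the 95% interval is t(0.975, 67) × 0.303 = 0.605. The noncentrality is b/0.303. Under a constant shift, coverage of the unshifted mean change is 1 minus the rejection probability, whatever that change is.

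| Assumed mean shift b | Noncentrality | Two-sided rejection | b as share of half-width | Coverage of 95% interval |
|---|---|---|---|---|
| 0 | 0 | 5.0% | 0% | 95% |
| 0.1 | 0.33 | 6.2% | 17% | 94% |
| 0.25 | 0.82 | 12.8% | 41% | 87% |
| 0.5 | 1.65 | 36.9% | 83% | 63% |

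The 0.1 row corresponds, for example, to one subject in five being reminded and moving by 0.5 point: 0.2 × 0.5 = 0.1.

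**With a pilot-sized change.** 6.2 − 2.7 = 3.5 points. If a 0.5-point shift were taken away, 3.0 would remain. The noncentrality is then 3.0/0.303 = 9.9 and power exceeds 99.9%. The test against zero is not in danger; the stated size of the change is.

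**Reach.** If the March 2020 end date (section 3.2) allows for the last 24-month visit, the last treatments fall around March 2018 and the last 90-day ratings around June 2018. The current text cites 2018 guidance and refers to subjects who have already finished the study (section 3.10.6). Many 90-day ratings may therefore already have been collected.

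**The case against.** The strongest reply is that this is one optional sentence with no shown use. It says only that a reminder may be given, and the form instructions and training that sites receive (sections 6.1 and 6.5.2) may make the practice clear. This stands as far as it goes: site practice is not visible in these documents. It does not remove the gap, because the protocol itself allows disclosure and does not require it to be recorded, so the plan gives no way to identify reminded subjects afterwards.

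A second reply is that the shifts are assumed, apply to any bias of that size, and are averages over everyone. This also stands. With few subjects reminded, the 0.1 row is nearer the mark than the 0.5 row. The 5% reference also presumes zero mean change without a device effect. Subjects are selected on a minimum score at the same rating that serves as baseline, so regression to the mean alone could produce change.

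A reader might infer that reminders are given at follow-up and inflate improvement. The documents support neither step. No section places a reminder at follow-up, and the direction is open: a wish to show benefit would enlarge the change, while anchoring on the old score would shrink it. A reader might equally infer that a reminder before treatment is harmless. That does not follow either, given the screening rating and the eligibility check.

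**Conclusion.** The concern holds as a minor point about how the primary endpoint is administered. The plan permits an earlier rTNSS to be disclosed around a rating, does not say when, and has no control arm against which any effect could be judged. It is not evidence of bias: neither the use of reminders nor the size or direction of an effect is known.

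The 6%, 13% and 37% rejection rates are conditional on an assumed average shift over all subjects, SD 2.5, 68 evaluable subjects and a mean change that is otherwise zero. They should not be read as the trial's false-positive rate. If the effect resembles the pilot's, what could suffer is the accuracy of the estimated change, not its significance. The sample size is unaffected.

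**What to change.** Replace the last sentence of section 3.11.3 with: *At every visit, including the procedure visit and phone visits, the subject rates the rTNSS without being shown or told any earlier score.* This covers both readings and the procedure-day rating. Record the date on which each site adopts it.

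For ratings already collected, ask each site whether reminders were given and at which visits, and report the answer with the primary result. If reminder status can be established by site or by subject, add a sensitivity analysis of the 90-day change by that status.

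The cost is one amended sentence, a site instruction, a short site query and, where possible, one extra analysis. No visits or subjects are added. The drawback is a small mid-study change in administration, which may slightly reduce comparability between earlier and later ratings. On the trial's timeline, the new wording may mainly protect the later exploratory ratings; for the primary endpoint the useful part is likely to be the site query and its disclosure.

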3.11.4. Rhinoconjunctivitis Quality of Life Questionnaire (RQLQ)

At baseline (pre-procedure) and post-procedure at the of the 90-day, 18 and 24 Month timepoints, the Rhinoconjunctivitis Quality of Life Questionnaire¹⁶ (RQLQ) will be administered. The RQLQ is a validated tool that measures the functional (physical, emotional, and social) problems associated with rhinitis. At baseline, subjects will select 3 activities and shall use the same 3 activities chosen during baseline RQLQ assessment for all subsequent RQLQ assessments.

3.11.5. Subject Satisfaction Questionnaire

A subject satisfaction questionnaire will be administered at the 90-day visit.

In order to evaluate changes in the subjects' usage of rhinitis medications, subjects' medication usage will be assessed at baseline and at each follow-up interval.

3.11.6. Subject Treatment Questionnaire

The Subject Treatment Questionnaire (STQ) is intended to better understand the subject's experience at the time of the treatment visit. The results of the STQ will be reviewed by the Sponsor to help understand the subject's experience.

The STQ will be administered via phone by an independent consultant, to ensure unbiased reporting of the patient experience.

The STQ will include a verbal report of subject's recall of occurrence of pain and/or discomfort, pain numeric rating scale (NRS)¹⁷, severity and duration reporting of pain and/or discomfort. The NRS utilizes an 11-point scale of zero to 10. Subjects verbally report pain on the scale of 0 to 10 with zero representing "no pain" and 10 representing "worst pain imaginable".

3.12. Concomitant Medications

Concomitant medication will be documented for all subjects for medication usage within thirty (30) days prior to consent and through duration of study participation. Medication collected should include, but is not limited to, medications taken for:

- any ENT, head and neck, respiratory, and/or airway related conditions or systems (i.e., rhinitis, allergies, asthma, migraines, antibiotic for sinusitis, GERD, etc.);
- medications due to a study-related Adverse Event; and
- any medication, as deemed by the investigator, to present a safety risk (i.e., anticoagulants, beta-blockers, etc.).

Subjects will be instructed to not use nasal anticholinergic sprays (e.g., Atrovent) beginning a minimum of 3 days prior to the procedure and throughout their study participation.

Additionally, subjects will be instructed to not take anti-coagulant medications for 2 weeks prior and 2 weeks following the procedure.

4. Adverse Events

4.1. Adverse Events

All adverse device effects (ADE) or procedure-related adverse events (AE) will be documented, including Unexpected Adverse Device Effects (UADE). Additionally, all Serious Adverse Events (SAE), regardless of device- and/or procedure-relatedness, and all ENT, head and neck, respiratory, and/or airway related AEs will be documented.

Adverse events (AE), as defined above, will be assessed continuously throughout the study. An adverse event is defined as any untoward medical occurrence in a subject, regardless of whether the event is related to the device or is a known risk.

Each Investigator shall be responsible for determination of the causal relationship of all adverse events from his/her investigational site to the device and/or procedure, as well as any pre-existing conditions. Each Investigator is responsible for monitoring the safety of the subjects enrolled. The Sponsor is responsible for the ongoing safety evaluation of the product(s) across all sites. The Sponsor shall determine whether an adverse event is reportable and will promptly notify all participating investigators and regulatory authorities, as appropriate, of findings that could affect adversely the safety of subjects, impact the conduct of the trial or alter the IRB's approval opinion to continue the trial.

4.1.1. Adverse Device Effect (ADE)

Any sign, symptom, or disease in a study subject that occurs during the course of a clinical trial that is determined by the investigator to have a causal relationship or possible causal relationship with the device under investigation.

4.1.2. Unanticipated Adverse Device Effect (UADE)

Any serious adverse effect on health and safety or any life-threatening problem or death caused by, or associated with a device, if that effect, problem, or death was not previously identified in nature, severity, or degree of incidence in the investigational plan or application, or

any other unanticipated serious problem associated with a device that relates to the rights, safety, or welfare of subjects.

4.1.3. **Serious Adverse Event (SAE)**

Any untoward medical occurrence in a subject, regardless of whether the event is related to the device that:

- a. results in death;
- b. results in a life-threatening illness or injury;
- c. results in a permanent impairment of a body structure or body function;
- d. requires in-patient hospitalization or prolongation of existing hospitalization
- e. results in medical or surgical intervention to prevent permanent impairment to body structure or function;
- f. results in fetal distress, fetal death, or a congenital abnormality/birth defect.

4.1.4. **Reportable Incidents**

Serious adverse events (SAEs) and unanticipated adverse device effects (UADEs) must be reported to the Sponsor within 24 hours of study site's knowledge of the event:

[name]
Arrinex, Inc.
[name]
[name]
[contact]
Email: [contact]

A full reporting of the event shall be provided within five (5) working days of knowledge of the event. The Sponsor is then responsible for notifying the IRB, as required.

5. **Statistical Analysis**

5.1. **Endpoints**

5.1.1. **Primary Endpoints**

- Safety as assessed by the incidence of procedure- or device-related serious adverse events (SAEs) and unanticipated adverse device effects (UADEs).
- Effectiveness as assessed by the mean change in nasal symptoms using the four-symptom rTNSS (reflective Total Nasal Symptom Score) at 90 days post-treatment.

5.1.2. **Secondary Endpoints**

- Incidence of device or procedure related adverse events

- Impact on quality of life assessed by the Rhinoconjunctivitis Quality of Life Questionnaire (RQLQ) at 90 days post-treatment

5.1.3. Exploratory Endpoints

- Effectiveness as assessed by the change in nasal symptoms using the four-symptom rTNSS (reflective Total Nasal Symptom Score) from baseline at all other follow-up points
- Treatment response as defined by $\geq 25\%$ and $\geq 50\%$ improvement in rTNSS scores
- Change in individual components of the rTNSS score
- Impact on quality of life assessed by the Rhinoconjunctivitis Quality of Life Questionnaire (RQLQ) at 18 months and 24 months post-treatment

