1.1. Background

Rhinitis is a very common condition throughout the world. In the United States alone, it affects 10-30% of the adult general population. This accounts for 30-60 million people in the United States and the prevalence has been increasing in recent decades, making it the fifth most common chronic disease in the US. Rhinitis is the inflammation of the nasal mucosa affecting patients with at least one of the following distressing symptoms: nasal congestion, rhinorrhea, sneezing, and nasal itching.

The current standard of care to control this disease starts with pharmacologic interventions, typically beginning with over the counter medications. Nasal steroids (i.e. Flonase, Nasonex) and oral anti-histamines (i.e. Claritin, Allegra, Zyrtec) are the mainstays of medical management. They have their challenges, however, as they require daily use and have limited effectiveness, especially against non-allergic rhinitis. Sedating anti-histamines such as Benadryl are used intermittently but the somnolent side effects are not usually well tolerated.

Prescription medications are used when OTC medication management fails. Oral steroids can be effective in the short term but carry more severe long-term side effects including immunosuppression, osteoporosis, Cushing syndrome and diabetes. Adrenergic agents such as Afrin are effective but quickly result in tolerance and “rebound” (recurrence and sometimes worsening of symptoms when off the medication).

When pharmacological treatments do not provide adequate response, surgical techniques have also been developed to treat rhinitis. These techniques include electrocautery, chemocautery, laser cautery, microdebrider turbineoplasty, radiofrequency ablation, subtotal turbinectomy, total inferior turbinectomy, and submucosal resection. These procedures primarily seek to address the nasal obstructive component through reduction of the inferior turbinate.

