1.4. Regulatory Status

The ClariFix™ device (K162608) is an FDA 510(k) cleared Class II cryosurgical tool indicated for the destruction of unwanted tissue during surgical procedures, including in adults with chronic rhinitis.

2. Risk/Benefit Analysis

The Sponsor has undertaken a comprehensive risk-benefit analysis.

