3.7. Subject Eligibility

To be eligible to participate, subjects must meet all of the inclusion criteria and none of the exclusion criteria listed in **Table 1**.

Table 1. Eligibility Criteria

Inclusion Criteria
 
 a) Subject is ≥ 21 years of age b) Subject has moderate to severe symptoms of rhinorrhea (individual symptom rating of 2 or 3), mild to severe symptoms of congestion (individual symptom rating of 1, 2 or 3) and a minimum rTNSS score of 4 (out of 12) at the time of the treatment visit. These symptoms shall have been present for > 6 months. c) Subject has had documented allergy test within the last 10 years that defines whether or not subject has allergies to perennial and seasonal allergens or is willing to have one performed prior to study exit. d) Subject has been dissatisfied with medical management, defined as usage of intranasal steroids for a minimum of 4 weeks without adequate symptom relief by the subject's assessment e) Subject has signed IRB-approved informed consent form

Exclusion Criteria
 
 a) Subject has clinically significant anatomic obstructions that in the investigator's opinion limit access to the posterior nose, including but not limited to septal deviation or perforation, nasal polyps, sinonasal tumor. b) Subject has had any prior sinus or nasal surgery that significantly alters the anatomy of the posterior nose. c) Subject has active nasal or sinus infection d) Subject has moderate to severe ocular symptoms e) Subject has a history of nosebleeds in the past 3 months f) Subject has a history of rhinitis medicamentosa g) Subject has had prior head or neck irradiation h) Subject has active coagulation disorder or is receiving anti-coagulants which cannot be safely stopped for 4 weeks (excluding aspirin) i) Subject is pregnant j) Subject is participating in another clinical research study k) Subject has an allergy or intolerance to anesthetic agent

- l) Subjects with cryoglobulinemia, paroxysmal cold hemoglobinuria, cold urticaria, Raynaud's disease, and/or, open and/or infected wounds at or near the target tissue
- m) Any physical condition that in the investigator's opinion would prevent adequate study participation or pose increased risk

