5.2.6. Sample Size Estimation and Assumptions

Assuming a two-tailed α -level of 0.05, and a standard deviation of the within-subject changes from baseline of 2.5, 68 evaluable subjects will yield 90% power to detect a one-point change in the 4-symptom rTNSS. To account for possible dropouts and protocol violations, the enrollment target will be a total sample size of N=100.

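### Later nasal procedures and repeat cryotherapy are neither specifically recorded nor handled in the analysis, so late exploratory scores may credit their effect to the first treatment

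*Combined protocol and SAP*

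**What the plan says.** **Endpoints and analysis.** Section 5.1.3 lists as exploratory the change in rTNSS "from baseline at all other follow-up points", response at two thresholds (25% and 50% improvement), the individual rTNSS components, and RQLQ at 18 and 24 months. The Efficacy set (Section 5.2.3) is every enrolled subject with at least one follow-up evaluation. The Per Protocol set removes subjects with deviations judged major, a term that is not defined. Section 5.2.5 adds: "No imputation of data will be performed". No section says what happens to scores taken after a further procedure.

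**Why later procedures are foreseeable.** Section 1.1 states: "When pharmacological treatments do not provide adequate response, surgical techniques have also been developed to treat rhinitis". It goes on to list several turbinate procedures. Inclusion criterion d requires that intranasal steroids gave too little relief. Section 1.4 says the study device "is an FDA 510(k) cleared Class II cryosurgical tool", with adults with chronic rhinitis inside the indication, so it could be used again outside the study.

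**What is restricted or recorded.** Nasal surgery appears only as an entry exclusion: "Subject has had any prior sinus or nasal surgery that significantly alters the anatomy of the posterior nose". The limit of two cooling cycles per side (Section 3.9.3) belongs to the treatment procedure itself. On-study restrictions (Sections 3.8 and 3.12) cover nasal anticholinergics, new categories of nasal spray, and anticoagulants around the procedure. Section 3.12 logs medicines: "Concomitant medication will be documented for all subjects for medication usage within thirty (30) days prior to consent", and from then on through participation. Table 2 has rows for medication but none for procedures. The only stated trigger for withdrawing a treated subject is pregnancy (Section 3.9.1).

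**The concern.** A subject whom the first treatment did not help is the one most likely to seek turbinate surgery or a second cryotherapy. If that second procedure works, the subject's later rTNSS falls, and the plan as written reports the fall as change after the study treatment. There is no control arm in which the same thing would happen and cancel out.

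The results at stake are those from day 180 to month 24, which readers will take as evidence of how long one treatment lasts. Section 1.2 gives durability as the purpose of the pilot's extended follow-up, so reading this study's late visits the same way is reasonable, although the protocol does not say so. The day-90 primary endpoint has the same gap, but over a much shorter window. Without a recorded procedure and date, an analyst cannot reliably identify the affected scores.

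**Working it through.** **1. The plan's own figure.** Section 5.2.6 opens with "Assuming a two-tailed α -level of 0.05" and uses "a standard deviation of the within-subject changes from baseline of 2.5", a one-point change and 90% power.
- Normal approximation: ((1.960 + 1.282) × 2.5 / 1)² = 65.7, so 66.
- Paired t-test with the noncentral t distribution: n = 67 gives power 0.897 and n = 68 gives 0.902.

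The stated 68 evaluable subjects are reproduced. Nothing below changes that number, the power or the alpha.

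**2. Is a later procedure barred, recorded or analysed?**
- Barred: no. The on-study restrictions name medicines only, and the surgery criterion looks backwards from entry.
- Recorded: not specifically. General health is reviewed from day 30 (Sections 3.10.3-3.10.5), a clinical evaluation is documented at study visits (3.11.1), and ENT-related adverse events and all SAEs are documented (4.1). None of these asks for a nasal procedure or its date. Elective surgery for persisting baseline symptoms is not named as an event.
- Analysed: no. The endpoint covers every other follow-up point, in everyone with one follow-up, with no rule for later procedures.

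**3. Size in the mean (illustration).** Let q be the share of subjects with a score at a late visit who have had a further procedure, and g the gain from it in rTNSS points. Assume these subjects had no benefit from the first treatment. The all-observed mean improvement is then overstated by q × g. The documents give neither q nor g, so both are assumptions. The upper value of g borrows the pilot's 90-day fall, 6.2 − 2.7 = 3.5 (Section 1.2).

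| q | g = 2.0 | g = 3.5 |
|---|---|---|
| 5% | 0.10 | 0.18 |
| 10% | 0.20 | 0.35 |
| 15% | 0.30 | 0.53 |

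For scale, the upper end is about half the one-point change used for planning at day 90.

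**4. Size in a responder rate.** If every such subject would otherwise be a non-responder and becomes a responder, the overstatement is at most q, that is 5-15 percentage points.

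**5. Would excluding post-procedure scores repair the mean?** Let m be the mean improvement in everyone else. Take q = 10%, m = 3.5 and g = 2.0.
- Mean effect of one treatment: (1 − q)m = 0.90 × 3.5 = 3.15.
- All observed scores: 3.15 + 0.10 × 2.0 = 3.35, overstated by 0.20.
- Post-procedure scores excluded, nothing imputed: m = 3.50, overstated by q × m = 0.35.
- Post-procedure change set to zero: 0.90 × 3.5 + 0.10 × 0 = 3.15, overstated by 0.

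With g = 3.5 the first two approaches tie at 0.35. Exclusion is worse whenever m exceeds g. The zero-change result is exact only because no first-treatment benefit was assumed. With partial benefit it would understate the effect.

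**The case against.** The strongest case against is that the stakes are limited. The only stated hypothesis concerns the 90-day mean change, and the results mainly affected are labelled exploratory. Using all observed scores whatever care follows is a recognised choice. The size above is wholly assumed, and the 3.5 points come from a first treatment in a small single-arm pilot, not from a second operation. Dissatisfied subjects may also decline the extension, which needs fresh consent after day 365; that would be a missing-data problem instead. All of this stands and limits the weight of the point. It does not answer it: an all-observed analysis can be interpreted only if the reader knows how many subjects had something else done.

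Some stronger readings are tempting, and the documents do not support them.
- A reader might infer that the bias can only favour the device. Section 2.2 lists swelling, increased congestion and scarring among the risks of cryosurgery, so a score taken after a repeat procedure could be worse.
- A reader might infer that such subjects necessarily stay in the Per Protocol set. No rule makes a later procedure a deviation, but major deviations are undefined, so their status is undetermined.
- A reader might infer that the information is irretrievable. Health review, clinical evaluation, and ENT event and medication records may reveal some procedures, though not reliably.
- A reader might infer that the plan specifies late responder rates. Section 5.1.3 gives thresholds but no time points for response.

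**Conclusion.** The point holds as a gap in recording and analysis. Over up to 24 months, later nasal or sinus procedures and repeat cryotherapy are not barred, not specifically recorded and not separately analysed. The exploratory late rTNSS and RQLQ results, and any late responder result, therefore credit post-procedure scores to the first treatment. The expected direction favours the device, but this is not certain.

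The size is unknown. The ranges of 0.10-0.53 points and up to 5-15 percentage points rest on an assumed 5-15% procedure rate, an assumed 2.0-3.5 point gain and no benefit from the first treatment. Nothing in the documents shows that any such procedure occurred. The sample size and the 90-day hypothesis test are not called into question. This is an inexpensive improvement worth making, not a flaw in the primary analysis.

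**What to change.** **Sections 3.10.2-3.10.5 and the CRFs:** at each visit, record any nasal or sinus procedure or repeat cryotherapy since Visit 2, with its date. For subjects already treated, ask retrospectively at the next contact.

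**Section 5.2.5, for the exploratory endpoints:**
- (a) count a subject as a non-responder at every time point after such a procedure;
- (b) report the cumulative number of subjects with a further procedure;
- (c) keep the all-observed mean change, and add a sensitivity result that replaces post-procedure scores with the last pre-procedure score or with zero change. State this as an explicit exception to "No imputation of data will be performed".

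Do not simply exclude post-procedure scores, for the reason shown in step 5 of the working.

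**Cost:** one CRF question with a date, a few lines of analysis text, and possibly a slightly less favourable late result. Sample size, power and alpha are unchanged, and no restriction on care is proposed.
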